8.3. Progression-free Survival

PFS is defined as the time from first dose to first occurrence of a disease progression or death, whichever comes first.

For patients who do not experience one of these events by the last date of study participation or the time of data cutoff, the following censoring rule will be used for PFS:

- Patients who do not experience disease progression or death and have an adequate post-baseline tumor assessment will be censored at the date of the last adequate tumor assessment that is SD or better.
- Patients who do not experience disease progression or death and do not have any adequate post-baseline tumor assessment that is SD or better will be censored at Day 1.

PFS (days) = date of event/censoring - date of first dose + 1.

PFS will be summarized by descriptive statistics (mean, standard deviation, minimum and maximum). The Kaplan-Meier method will be used to estimate the distribution functions of PFS per RECIST 1.1 and irRC, respectively. The quartiles, median along with 95% CI of PFS, and probability of being event free at selected time points will be provided. Kaplan-Meier plot of PFS (per RECIST 1.1 and irRC, respectively) will be provided for Arm A regardless of mRNA 2416 dose level in each study phase.

Kaplan-Meier plot of PFS (per RECIST 1.1 and irRC, separately) will be provided for Arm B regardless of mRNA 2416 dose level in each study phase.

8.4. Disease Control Rate

DCR is defined as the proportion of patients whose best overall response is CR, or PR, or had durable SD which is defined as there is at least 55 days between the first dose date and the last SD assessment date, and no PD between. All tumor response will be based on the investigators' assessment RECIST v1.1. DCR will be summarized with Clopper-Pearson 95% CI calculated for Phase II.

9. Safety Analysis

Safety evaluations will be based on the incidence, severity, and type of AE; serious AE; laboratory results; vital signs; electrocardiogram (ECG); ECOG performance status; and analysis of anti-drug antibodies. All safety analyses will be conducted on the safety set by treatment arm and dose cohort of mRNA-2416 (as specified in [Section 3.3](#)), and total for each treatment arm combining Phase I and Phase II. All safety data will be presented in listings based on the safety set.

9.1. Adverse Events

An AE is any adverse experience in a patient administered a pharmaceutical product, whether or not it is considered drug related, that occurs during a patient's study participation (defined as after a patient signs the informed consent form through the patient's last safety follow up visit or study discontinuation, whichever is later). A treatment-emergent AE (TEAE) is defined as any AE that newly appeared, increased in frequency, or worsened in severity occurring on or after the first dose of study drug.

Missing or partial start dates for AE data will be handled following the imputation rules of missing or partial start dates for concomitant medications data ([Section 7.1](#)). No imputation will be applied to the missing or partial stop dates for AEs. If the AE end date is complete and the partial AE start date imputed by the rules above is after the AE end date, then the start date will be imputed by the AE end date.

All AEs will be coded according to the latest version of MedDRA at the time of coding. The severity will be defined according to the NCI CTCAE version 4.03. If a patient experiences the same AE more than once with different toxicity grades, then the event with the highest grade will be tabulated in "by grade" tables. In addition, AEs with a missing intensity will be presented in the summary table as an intensity category of "Missing" only if the same event category has no other valid grades. AEs with missing relationship to the treatment will be imputed as treatment-related and summarized in the tables.

The incidence of AEs will be summarized in tables with the number and percentage of patients with AEs by system organ class (SOC) and preferred term (PT). Unless otherwise specified, at each level of SOC or PT, a patient with multiple events will only be counted once per SOC or PT. Percentages of patients with AEs will be calculated out of the number of patients in the safety set. Tables will be sorted by SOC in internationally agreed order, and PT within each SOC will be presented in descending frequency based on the total of Arm B combining Phase I and Phase II.

The following categories of AE will be summarized by SOC and PT:

- TEAEs
- TEAEs by maximum NCI CTCAE grade
- mRNA-2416-related TEAEs
- Durvalumab-related TEAEs
- TEAEs by relationship with mRNA-2416
- TEAEs by relationship with durvalumab
- Serious TEAEs
- TEAEs leading to discontinuation of mRNA-2416
- TEAEs leading to discontinuation of durvalumab
- TEAEs of special interest for durvalumab

An overview table of the following categories will also be provided:

- TEAEs
- TEAEs with NCI CTCAE grade ≥ 3
- mRNA-2416-related TEAEs
- Durvalumab-related TEAEs
- Serious TEAEs
- TEAEs leading to discontinuation of mRNA-2416
- TEAEs leading to discontinuation of durvalumab
- TEAEs of special interest for durvalumab
- TEAEs leading to death

All AEs will be presented in a data listing and TEAEs will be flagged in the listings. AEs leading to discontinuation of mRNA-2416, AEs leading to discontinuation of durvalumab, AEs leading to death, and SAEs will be presented in separate listings.

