Study Drug, Dosage and Route of Administration	mRNA-2416 will be administered to patients as intratumoral injections on Days 1 and 15 of each 28-day cycle (± 2 days). All patients in Arm B and Arm A patients that are to receive intratumoral injections to visceral lesions will reduce dosing frequency to every 4 weeks after completing 1 cycle of therapy (Day 1 and Day 15 for Cycle 1, then Day 1 only for Cycles 2-6).

	
The starting dose is 1.0 mg mRNA-2416 for Arm A and 4.0mg mRNA-2416 in combination with 1500mg of durvalumab for Arm B; other dose levels may be evaluated during this trial.

Randomization	Not applicable
Efficacy Assessments	Best response will be determined for each patient in accordance with RECIST/Cheson and irRC/LYRIC guidelines.
Safety Assessments	
Safety measures will include:
 
• AEs (including imAEs and AESIs)• Hematology, clinical chemistry, and liver function tests• 12-Lead electrocardiograms• Physical examination• Vital signs and body weight• Concomitant medications/procedures• ECOG performance status• Antibodies against OX40L, the protein translated by the drug product, will be reviewed with investigators as data are available 
Where applicable, AEs will be classified according to the NCI CTCAE Version 4.03.

Biomarker & Pharmacodynamic Assessments	The biomarker analysis will be used to investigate the effect of mRNA-2416 alone and in combination with durvalumab, as well as to determine how the markers are associated with clinical outcome. Immune responses will be studied in the peripheral circulation and in tumor biopsy specimens. Tumor biopsies will be examined using methods such as immunohistochemistry, quantitative immunofluorescence, RNA sequencing, and/or electrochemiluminescence (ECL) assays to evaluate changes in key immune pathway axes, such as PD-L1/PD-1 and OX40L/OX40, as well as characterization (eg, phenotype, distribution, and activation) of tumor infiltrating lymphocyte and myeloid populations. Cytokines will also be examined in both tumor and blood tissues using methods such as RNA sequencing and enzyme-linked immunosorbent assay (ELISA)/ ECL assays respectively.
Patient Reported Outcome Assessments	None
Statistical Procedures	Described in Section 13 and in the Statistical Analysis Plan

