Endocrinopathies involving thyroid or pituitary glands or adrenal insufficiency	none	Excludes events that are managed with or without systemic corticosteroid therapy and/or hormone replacement therapy and the patient is asymptomatic	
Type I diabetes mellitus	none	Events that are not managed with appropriate diabetic therapy	
Nephritis	none	Any immune-mediated increase in creatinine >3×ULN, or >3×baseline for patients with a baseline creatinine elevated above ULN	DLT
Elevated amylase or lipase/pancreatitis	none	Elevations in amylase or lipase >2.0×ULN with signs or symptoms of pancreatic inflammation	
All other imAEs OR non-imAEs	none	Events that do not resolve to Grade 1 or baseline within 30d	DLT
Infusion-related reactions	none	Events that do not resolve within 6h despite appropriate medical management.	DLT

- Any Grade ≥ 3 immune or non-immune adverse event (AE) that is at least possibly related to the investigational product (IP) or investigational regimen (IR) with two exceptions: Any grade of vitiligo or alopecia
- Hematologic toxicity:
 - Grade ≥ 3 neutropenia complicated by fever $>38.3^{\circ}\text{C}$
 - Grade 4 neutropenia (lasting more than 7 days)
 - Grade ≥ 3 thrombocytopenia with significant bleeding
 - Grade 4 thrombocytopenia (regardless of duration)
 - Grade 4 anemia (regardless of duration)

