12.1.5 DURVALUMAB ADVERSE EVENTS OF SPECIAL INTEREST

An AE of special interest (AESI) is one of scientific and medical interest specific to understanding of the IP and may require close monitoring and rapid communication by the investigator to the Sponsor. An AESI may be serious or non-serious. The rapid reporting of AESIs allows ongoing surveillance of these events in order to characterize and understand them in association with the use of this IP.

AESIs for durvalumab include, but are not limited to, events with a potential inflammatory or immune-mediated mechanism and which may require more frequent monitoring and/or interventions such as steroids, immunosuppressants, and/or hormone replacement therapy. These AESIs are being closely monitored in clinical studies with durvalumab monotherapy and combination therapy. An imAE is defined as an AESI that is associated with drug exposure and is consistent with an immune-mediated mechanism of action and where there is no clear alternate etiology. Serologic, immunologic, and histologic (biopsy) data, as appropriate, should be used to support an imAE diagnosis. Appropriate efforts should be made to rule out neoplastic, infectious, metabolic, toxin, or other etiologic causes of the imAE.

If the investigator has any questions with regards to an event being an imAE, the investigator should promptly contact the Study Physician.

AESIs observed with durvalumab include the following:

- Diarrhea/colitis and intestinal perforation
- Pneumonitis/ILD
- hepatitis/transaminase increases
- Endocrinopathies (ie, events of hypophysitis/hypopituitarism, adrenal insufficiency, hyper- and hypothyroidism and type I diabetes mellitus)
- Rash/dermatitis
- Nephritis/blood creatinine increases
- Pancreatitis/serum lipase and amylase increases
- Myocarditis
- Myositis/polymyositis
- Neuropathy/neuromuscular toxicity (eg, Guillain-Barré syndrome, and myasthenia gravis)

- Other inflammatory responses that are rare and/or less frequent with a potential immune-mediated etiology include, but are not limited to, pericarditis, sarcoidosis, uveitis and other events involving the eye, skin, hematological, and rheumatological events.

In addition, infusion-related reactions, and hypersensitivity and/or anaphylactic reactions with a different underlying pharmacological etiology are also considered AESIs.

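### In Arm B the planned AE tables do not, in general, give the incidence of multi-term durvalumab AESI categories or of TEAEs related to either drug

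*SAP*

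**What the plan says.** SAP 9.1 introduces ten TEAE summaries with "The following categories of AE will be summarized by SOC and PT". One of them is "TEAEs of special interest for durvalumab". Four concern causality: mRNA-2416-related TEAEs, durvalumab-related TEAEs, "TEAEs by relationship with mRNA-2416" and "TEAEs by relationship with durvalumab". The counting rule is that "a patient with multiple events will only be counted once per SOC or PT".

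A separate overview table has one line for any durvalumab AESI and one related line for each drug. Its Grade 3 or higher and serious lines are given regardless of relationship. All AEs are also listed by patient.

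Protocol 12.1.5 sets out AESIs as medical categories. Many join a diagnosis to a laboratory finding or group several conditions, for example "Pancreatitis/serum lipase and amylase increases". Hepatitis is likewise paired with transaminase increases, nephritis with creatinine increases, and rash with dermatitis. The endocrinopathy category names hypophysitis, adrenal insufficiency, thyroid disorders and type I diabetes. The list is expressly not exhaustive. Protocol 12.3 has the investigator judge causality for each study drug.

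The SAP does not say how a PT is assigned to an AESI category, or how AESIs are identified at all.

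**The concern.** The protocol describes durvalumab toxicity by category, and the SAP counts it by PT. A patient with two terms of one category appears in two PT rows, and no row holds the category. Causality has the same structure: a patient may have events attributed to mRNA-2416, to durvalumab, or to both, and the two single-drug counts do not show the overlap.

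Two numbers that a reader of a combination study would want are therefore not planned: how many Arm B patients had, say, any hepatic AESI, and how many had any TEAE attributed to at least one of the two drugs. The Arm B DLT criteria (Protocol 8.4.2) and the toxicity guidance (Protocol Appendix E) also work by category and by regimen, so the tables use a different unit from the rest of the protocol. If the grouping is left until after the open-label data have been seen, the choice of terms in each category is made with the results in view.

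**Working it through.** The plan states no figure to reproduce. The check is what the planned rows allow a reader to deduce.

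**Inputs**
- Patients are counted once within a PT row and once within a SOC row, not across the PTs or SOCs that form a category (SAP 9.1).
- Relatedness is tabulated for each drug, with no either-drug line (SAP 9.1).
- N = 45, the planned Arm B expansion enrolment (SAP 4.1), is used only as a convenient denominator. The Arm B total in the safety tables combines Phase I and Phase II (SAP 9).
- All event counts below are assumed.

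**Formula.** If k rows hold c1, ..., ck patients out of N, the number of patients in at least one row lies between max(c1, ..., ck) and min(N, c1 + ... + ck).

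**AESI category spread over three PT rows, N = 45**
- Counts 4, 3, 2: from 4 (4/45 = 8.9%) to 4 + 3 + 2 = 9 (9/45 = 20.0%).
- Counts 3, 2, 1: from 3 (6.7%) to 6 (13.3%).
- One PT row with 2 patients: exactly 2 (4.4%).

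**TEAEs related to either drug, N = 45**

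| mRNA-2416-related | Durvalumab-related | Either drug, patients | Either drug, % |
|---|---|---|---|
| 18 | 14 | 18 to 32 | 40.0 to 71.1 |
| 9 | 9 | 9 to 18 | 20.0 to 40.0 |
| 27 | 9 | 27 to 36 | 60.0 to 80.0 |
| 6 | 0 | 6 | 13.3 |

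In the first case the number with TEAEs related to both drugs lies between max(0, 18 + 14 - 45) = 0 and 14.

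With N = 41 the first relatedness case becomes 43.9% to 78.0%, and the 4, 3, 2 category becomes 9.8% to 22.0%.

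**What other planned rows add**
- No category can exceed the any-AESI line in the overview. If that line were 6, the 4, 3, 2 category would be capped at 6/45 = 13.3%, so the range would be 8.9% to 13.3%.
- A SOC row in the AESI table equals the category count when the category lies wholly in that SOC and is the only AESI there. If only the first condition holds, the SOC row is an upper cap.
- The either-drug count cannot exceed the any-TEAE line. That cap does little if nearly every patient has a TEAE.

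These rows can tighten a range, and sometimes close it, but nothing in the plan ensures that they do.

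**The case against.** The strongest reply is that SOC and PT tables are the conventional layout and meet what the protocol asks. Protocol 13.4.2 calls for TEAEs by SOC, PT, severity and relationship to study drug, without saying how two drugs are to be combined. Per-drug tables follow naturally from per-drug causality. That stands: this is not a departure from the protocol.

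A reader might also infer more than the documents support:
- *That no AESI category can be read.* Myocarditis is named as a single condition, and its PT row would give the count if it codes to one PT. Total AESI incidence is in the overview.
- *That the tables cannot narrow the ranges.* They can, as shown above.
- *That AESIs are not graded.* The table by maximum CTCAE grade covers every TEAE by PT, so AESI terms appear there. Only grade by category is missing.
- *That the Phase I primary endpoint is not delivered.* It is the incidence, nature and severity of AEs and SAEs. It names neither AESI categories nor relatedness, and the planned TEAE tables serve it.
- *That dose decisions are affected.* The Safety Review Committee works from all available safety data and patient-level DLT rules, not from this table.

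Two planned outputs cover part of the gap. The DLT table reflects toxicity at least possibly related to study therapy (Protocol 8.4.2), but only over the first 28 days, whereas durvalumab may run to 24 months in total. The listings allow either count to be rebuilt, but not with a grouping fixed in advance.

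**Conclusion.** The point holds as a worthwhile and inexpensive improvement, not as an error. In Arm B the incidence of AESI categories that span several PTs or SOCs, and of TEAEs related to either drug, cannot in general be read from the planned tables.

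How much is left open depends on the overlap. With the assumed counts the ambiguity is 20.0 - 8.9 = 11.1 percentage points for one category and 71.1 - 40.0 = 31.1 points for relatedness, before any narrowing by other rows. These are illustrations and not forecasts.

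The conclusion assumes that categories such as hepatitis/transaminase increases, endocrinopathies and rash/dermatitis code to more than one PT. The documents contain no coding map, but the category names point that way. The underlying data are collected and no error rate or decision rule changes.

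**What to change.** In SAP 9.1:

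1. Summarise durvalumab AESIs with the Protocol 12.1.5 category as the first level and PTs nested below. Count each patient once per category and show maximum CTCAE grade. Use a PT-to-category list fixed before database lock, which also settles how AESIs are identified.
2. For Arm B, add *TEAEs related to mRNA-2416 and/or durvalumab* to the SOC/PT tables and the overview, overall and for Grade 3 or higher and serious events. Derive it from the two per-drug assessments after the SAP's existing rule for missing relationship. A footnote should say that it includes the single-agent durvalumab period.
3. Show immune-mediated AEs as a subset only if the CRF already records that judgement. The definition in Protocol 12.1.5 needs case-level assessment, and the CRF is not among the documents.

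Items 1 and 2 cost SAP wording, a term list that needs some clinical decisions because the protocol's list is open-ended, and a few added rows. They need no new data and no change to sample size, alpha or power. Each range above then becomes one exact count.

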9.1.1. Dose-limiting Toxicity

The DLT window of observation will be the first 28 days of mRNA-2416 treatment and meets the following criteria:

- All Grade 3 AEs with the exception of the following:
 - Grade 3 thrombocytopenia lasting <7 days

- Grade 3 neutropenia without fever or lasting <7 days
- Any Grade 4 or Grade 5 toxicity

Death due to disease progression is not considered a DLT.

A summary table of DLTs will be presented, including number and percentage of patients for each PT based on the safety set and will be sorted in descending frequency based on the total of Arm B combining Phase I and Phase II.

All DLT events will be presented in a listing.

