8.4.2 DEFINITION OF DOSE-LIMITING TOXICITIES

A dose-limiting toxicity (DLT) is defined as an adverse event or abnormal laboratory value assessed as unrelated to disease, disease progression, inter-current illness, or concomitant medications and at least possibly related to the study therapy and that occurs within the first 28 days of study therapy. The investigator must notify the Sponsor immediately of any DLTs.

For patients in Arm A receiving mRNA-2416, the following toxicities will be considered a DLT:

- All Grade 3 AEs with the exception of the following:
 - Grade 3 thrombocytopenia lasting <7 days
 - Grade 3 neutropenia without fever or lasting <7 days
- Any Grade 4 or Grade 5 toxicity. Death due to disease progression is not considered a DLT.

For patients in Arm B receiving mRNA-2416 in combination with durvalumab, the following toxicities will be considered a DLT:

Adverse Event (AE)+C2:F16	DLT Criteria		
	Grade 2 Events	Grade 3 Events	Grade 4 events
Diarrhea/colitis	none	Events that do not resolve to Grade 1 or baseline within 14 d (whether or not it is immune-mediated)	DLT
Pneumonitis	Non-infectious pneumonitis that does not resolve to Grade ≤1 within 10 days	Non-infectious pneumonitis is a DLT	DLT
Hepatitis	none	Alanine aminotransferase (ALT) or aspartate aminotransferase (AST) >8×ULN or total bilirubin (TBL) >5×ULN OR events meeting Hy's Law (AST or ALT ≥3×ULN with concurrent increase in TBL ≥2×ULN without evidence of cholestasis or alternative explanations)	DLT
Rash	Any grade rash with bullous formation.	Rash not resolving to Grade 1 or baseline within 30d. Any rash with bullous formation.	DLT
Peripheral neuromotor syndromes such as Guillain-Barre or myasthenia gravis	Events not resolving to Grade 1 within 30d. Events with any signs of respiratory insufficiency or autonomic instability.	Events that do not resolve to Grade 1 within 30d. Events with any signs of respiratory insufficiency or autonomic instability.	DLT
Myocarditis	Events that do not resolve to Grade 1 within 3d OR a biopsy confirms immune-mediated myocarditis.	All Grade 3 myocarditis.	DLT
Myositis/polymyositis	Events that do not resolve to Grade 1 within 30d OR exhibit signs of respiratory insufficiency regardless of optimal medical management	Events that do not resolve to Grade 1 within 30d OR exhibit signs of respiratory insufficiency regardless of optimal medical management	DLT

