In addition to the information presented in the statistical methods section of the protocol (Section 13) which provides the principal features of planned analyses for this study, this SAP provides appropriate statistical analysis methodologies in details. It also documents modifications or additions (if applicable) to the analysis plan that are not “principal” in nature and result from information that was not available at the time of protocol finalization.

PPD Biostatistics and Programming team, designee of Moderna Biostatistics and Programming department, will perform the statistical analysis of the efficacy, safety, pharmacokinetic, and pharmacodynamics; Statistical Analysis System (SAS) Version 9.4 or higher will be used to generate all statistical outputs (tables, figures, listings, and datasets). The SAP will be finalized and approved prior to the clinical database lock for primary analysis. If the methods in this SAP differ from the methods described in the protocol, the SAP will prevail.

2. Study Objectives

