3.2. Study Endpoints

3.2.1. Primary Endpoints

The primary endpoints of the study are as follows:

Phase I

- Incidence and nature of dose-limiting toxicities (DLTs) with mRNA-2416 alone and in combination with durvalumab
- Incidence, nature, and severity of adverse events (AEs)/serious adverse events (SAEs), graded according to the National Cancer Institute (NCI) Common Terminology Criteria for Adverse Events (CTCAE) Version 4.03 for mRNA-2416 alone and in combination with durvalumab

Phase II

- Assessment of objective response rate mRNA-2416 alone and in combination with durvalumab in patients with ovarian cancer based on RECIST v1.1

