11.6. Statistical Analysis of Pharmacokinetic Parameters

Pharmacokinetic parameters derived from serum concentrations will be individually listed and summarized. The PK parameters with the exception of t_{\max} will display n, mean, standard deviation, CV, geometric mean, median, minimum, and maximum as descriptive statics. However, t_{\max} will only display n, median, minimum and maximum.

For the listings, concentration data will be presented to the same precision as the data is received. All PK parameters will be presented in the listings to 3 significant figures with the exception of t_{\max} , which will be presented to 2 decimal places.

For summary statistics, the following precisions should be used:

- n should be presented to zero decimal places
- CV% should be presented to 1 decimal place
- Mean, standard deviation, geometric mean, median, minimum, and maximum should be presented to the same precision as the listings

12. Interim Analysis

No formal interim analysis is planned.

13. Changes in the Planned Analysis

One of the exploratory endpoints, assessment of the correlation of other investigational serum-based proteins (e.g., anti-drug antibodies) with PK, efficacy, and safety, is not included in this statistical analysis plan.

14. References

Eisenhauer EA et al. New response criteria in solid tumours: revised RECIST guideline (version 1.1). *Eur J of Cancer.* 2009; 45(2):228-247.

DocuSign Envelope ID: B20D66AA-D718-4BD5-9F79-8CFF4FE948CA

Statistical Analysis Plan (SAP) Client Approval Form

Client:	ModernaTX, Inc.
Protocol Number:	mRNA-2416-p101
Document Description:	Final Statistical Analysis Plan
SAP Title:	A Phase I/II, Open-label, Multicenter, Dose Escalation and Efficacy Study of mRNA-2416, a Lipid Nanoparticle Encapsulated mRNA Encoding Human OX40L, for Intratumoral Injection Alone and in Combination with Durvalumab for Patients with Advanced Malignancies
SAP Version Number:	1.0
Effective Date:	29NOV2021
Author(s):	
For PPD: PPD	
For Moderna: PPD	
Approved by:	
PPD	Date (DD-MMM-YYYY)
Biostatistics and programming, PPD	
PPD	Date (DD-MMM-YYYY)
Clinical Development, Moderna, Inc.	
PPD	Date (DD-MMM-YYYY)
Biostatistics, Moderna, Inc.

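### SAP 9.1.1 reports Arm B DLTs against the protocol's Arm A list, so the reported Phase I primary endpoint can differ from the protocol's own DLT count

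*SAP*

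**What the plan says.** DLT incidence is a Phase I primary endpoint for both regimens (SAP 3.2.1): "Incidence and nature of dose-limiting toxicities (DLTs) with mRNA-2416 alone and in combination with durvalumab".

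Protocol 8.4.2 first sets conditions common to both arms. The event must be at least possibly related to study therapy, not attributable to disease, intercurrent illness or other medication, and within the first 28 days. It then gives two definitions. One opens "For patients in Arm A receiving mRNA-2416, the following toxicities will be considered a DLT" and is the short list of Grade 3 events with two hematologic exceptions, plus Grade 4 and 5. The other opens "For patients in Arm B receiving mRNA-2416 in combination with durvalumab, the following toxicities will be considered a DLT" and consists of a 13-row table with Grade 2, 3 and 4 columns, a bullet making related Grade ≥3 events DLTs except vitiligo or alopecia, and a hematologic list.

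SAP 9.1.1 has one definition, beginning "The DLT window of observation will be the first 28 days of mRNA-2416 treatment and meets the following criteria". Its criteria are those of the Arm A list, including the exemption for "Grade 3 thrombocytopenia lasting <7 days". The resulting table covers Arm B, since it is to be "sorted in descending frequency based on the total of Arm B combining Phase I and Phase II". SAP section 1 adds: "If the methods in this SAP differ from the methods described in the protocol, the SAP will prevail". SAP section 13 declares a single change, unrelated to DLTs: "One of the exploratory endpoints, assessment of the correlation of other investigational serum-based proteins".

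**The concern.** The SAP carries the monotherapy definition over to the combination arm without saying so. The Arm B criteria were written for a checkpoint inhibitor: they count certain immune-mediated toxicities below Grade 3, and all five event types concerned are named durvalumab AESIs in protocol 12.1.5. A table built from the Arm A list would leave out of the Arm B DLT count exactly these events.

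What is at stake is the agreement of two counts. The Safety Review Committee (SRC) counts DLTs under protocol 8.4 to decide escalation and the MTD. The study report would tabulate DLTs under SAP 9.1.1. For the same patients these can differ, and the SAP's precedence clause gives the programmer no reason to go back to the protocol.

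**Working it through.** The documents give no DLT rate or power figure to reproduce here, so the check is a comparison of rules followed by counts for stated cases.

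**1. Grade 2 column.** Five of the 13 Arm B rows have an entry there: non-infectious pneumonitis unresolved at 10 days; bullous rash of any grade; peripheral neuromotor syndromes and myositis (unresolved at 30 days, or with respiratory signs; for neuromotor syndromes also autonomic instability); and myocarditis (unresolved at 3 days, or biopsy-confirmed). The SAP list starts at Grade 3, so it captures 0 of 5.

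**2. Hematologic events.** In Arm B, Grade ≥3 thrombocytopenia with significant bleeding is a DLT. The SAP exempts the Grade 3 case if it lasts under 7 days, unless the bleeding is itself recorded as a Grade ≥3 AE. In Arm B, Grade ≥3 neutropenia with fever above 38.3°C is a DLT. The SAP exempts Grade 3 neutropenia that is afebrile or short; read literally, the second branch exempts a febrile case lasting under 7 days.

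**3. Relatedness.** SAP 9.1.1 does not repeat the relatedness condition. It excludes only death from disease progression. An unrelated Grade 3 AE in the first 28 days therefore meets the SAP list, in either arm.

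**4. Counts.** Suppose two of six Arm B patients have the event, with onset by Day 28, and related except in the last row. No event rates are assumed. The MTD rule in 8.4.3 requires fewer than 2 of 6, so 2/6 = 33% exceeds it and 0/6 does not.

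| Event in two of six patients | Protocol, all Arm B rules applied | Protocol, table and hematologic list govern | SAP list |
|---|---|---|---|
| Grade 2 myocarditis, biopsy-confirmed | 2/6 | 2/6 | 0/6 |
| Grade 2 non-infectious pneumonitis, unresolved at 10 days | 2/6 | 2/6 | 0/6 |
| Grade 2 bullous rash | 2/6 | 2/6 | 0/6 |
| Grade 3 thrombocytopenia, 5 days, significant bleeding | 2/6 | 2/6 | 0/6, or 2/6 if the bleeding is its own Grade ≥3 AE |
| Grade 3 neutropenia with fever above 38.3°C, under 7 days | 2/6 | 2/6 | 0/6 on a literal reading |
| Grade 3 non-bullous rash, resolved in 3 days | 2/6 | 0/6 | 2/6 |
| Managed, asymptomatic Grade 3 endocrinopathy | 2/6 | 0/6 | 2/6 |
| Afebrile Grade 3 neutropenia, 10 days | 2/6 | 0/6 | 0/6 |
| Unrelated Grade 3 AE | 0/6 | 0/6 | 2/6 |

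In the first five rows and the last, the SAP departs from the protocol however the protocol is read, subject to the qualification shown for thrombocytopenia.

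**5. Why there are two protocol columns.** In 11 of the 13 Arm B rows (all but pneumonitis and myocarditis) the Grade 3 cell sets a limit: a resolution time, laboratory value, symptom or management condition. The bullet below counts every related Grade ≥3 event except vitiligo or alopecia. If everything is applied together, the count is determinate and conservative, but those 11 limits do nothing, and the endocrinopathy row's exclusion of managed, asymptomatic events is contradicted outright. The hematologic list's condition that Grade 4 neutropenia last more than 7 days likewise conflicts with the bullet and with the Grade 4 cell of the catch-all row. Sections 8.4.2 to 8.4.4 and 8.2.7 do not say which rule governs.

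**6. Pending events.** Four Grade 2 rows carry a time limit. With onset on Day d and a limit of k days, the event is undecided at Day 28 when d + k > 28. For k = 3 (myocarditis) that is Days 26–28; for k = 10 (pneumonitis), Days 19–28; for k = 30 (neuromotor, myositis), every onset day, with the limit passing on Days 31–58. Section 8.4.4 sets a minimum wait, so the SRC may wait longer, but no text says how to count an undecided event.

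**The case against.** The strongest reply is that the table may never be programmed from these criteria. A DLT call needs clinical judgment on cause, investigators must report DLTs to the Sponsor at once, and the SAP is built on a case report form that is not among the documents. If reported DLTs feed the table, the Grade 2 events will appear. That stands as a limit on certainty. It does not repair the SAP, which states criteria, states the wrong ones for Arm B, and nowhere says that reported DLTs are the source.

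A second reply is that little follows. A reader might infer that the SAP changes the MTD or exposes patients to a wrong dose. The documents do not support that: the SRC decides cohort by cohort under protocol 8.4, while the SAP governs the analysis. Nor would the toxicities vanish from the report. They would still appear in the TEAE tables, the durvalumab AESI table and the AE listings, though not as DLTs.

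A third reply concerns the denominators. The SAP table uses the safety set, whereas the dose decision uses DLT-evaluable patients, so percentages could differ even with the right definition. That is correct, and the six-patient counts above are illustrations, not forecasts.

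On the protocol ambiguity, a reader might infer that it sends patients to an unsafe dose. Two transient related Grade 3 events in the first three patients at 4 mg are 2/3 when all rules apply, which exceeds the MTD. They are 0/3 only if the table's limits govern, and even then 8 mg is permitted subject to SRC consensus, not compelled.

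**Conclusion.** The SAP point holds as a reporting error in a Phase I primary endpoint, and should be corrected before the DLT table is produced. The mismatch of definitions is certain from the text. Under the listed criteria, Arm B DLTs are under-counted for five event types below Grade 3 and for two short-lived Grade 3 hematologic situations (one qualified, one on a literal reading), and can be over-counted through the missing relatedness condition. In a six-patient cohort the gap can be 2/6 against 0/6, which straddles the protocol's MTD limit. That the printed table would be wrong rests on one assumption: that it is built from the criteria in 9.1.1. The error does not set the MTD.

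The conflict inside protocol 8.4.2 is secondary, a clarification. The inclusive reading is workable and conservative, but the text should not leave it to be inferred.

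**What to change.** **SAP 9.1.1.** Define DLTs by arm by reference to protocol 8.4.2: the Arm A list for Arm A; the Arm B table, Grade ≥3 bullet and hematologic list for Arm B. Restore the relatedness condition for both arms. If investigator-reported DLTs are to be the source, say so. Cost: one subsection, with no new patients or data.

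**Protocol 8.4.2, Arm B.** State that any related Grade ≥3 event, including Grade 5, is a DLT except vitiligo or alopecia. Delete the conflicting Grade 3 limits in the table and the 7-day condition for Grade 4 neutropenia. The reverse choice, letting the table govern the events it names, should be avoided: the table has no Grade 5 column, so a fatal pneumonitis or myocarditis would have no stated criterion, and transient related Grade 3 events would stop counting. The recommended wording makes Arm B stricter than Arm A for short Grade 3 cytopenias, as the bullet already does.

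**Timed Grade 2 rows.** State either that an event unresolved at cohort review counts as a DLT, or that the decision waits until the limit has passed.

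The two protocol changes fit in one short amendment, which under section 15.2 needs Sponsor approval before IRB approval is sought. Waiting for a 30-day limit could delay a cohort decision until as late as Day 58; counting the event at review avoids that.
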